1.8 Correlative Studies Background

Molecular profiling has identified various phenotypes of GBM. It has already been shown that the methylation status of the MGMT promoter is an important prognostic factor in predicting survival with alkylating therapy (33). More recently, The Cancer Genome Atlas (TCGA) Network catalogued recurrent genetic abnormalities in GBM, and established the existence of 4 subtypes (proneural, neural, classical, and mesenchymal) (34). Aberrations and gene expression of *EGFR*, *NF1*, and *PDGFR α /IDH1* each define classical, mesenchymal, and proneural, respectively. Gene signatures of normal brain cell types showed a strong relation between subtypes and different neural lineages. Additionally, response to aggressive therapy differs by subtype with greatest benefit in classical and no benefit in proneural (34). Given the differences in sensitivity to the combination of sorafenib and valproic acid in preclinical models, it will be important to characterize patient tumors, as this combination may be effective in one subtype of GBM but ineffective in another. PDGFR α is a target of sorafenib, and expression of this protein may predict drug efficacy. This study will evaluate PDGFR α levels in tumor specimens by immunohistochemistry (IHC), and correlate this sorafenib drug target to response. Consideration will be given to gene expression profiling at the conclusion of the study, based on responses to therapy. This may help to further characterize the patient population to be targeted in a phase 3 study.

1.9 Rationale for Adaptive Design

All patients with recurrent or progressive high-grade glioma will be eligible for the study. Sorafenib is a multikinase inhibitor, with a wide variety of cellular effects. Not enough is known about the *in vivo* mechanisms of action and resistance to the drug to justify initial exclusion of molecular subtypes of high-grade glioma. There will be an interim analysis, however; at which point the decision will be made whether or not to continue with all subtypes of high-grade glioma, based on pre-specified efficacy criteria. If efficacy criteria are not met for the combined group, the study will continue with only patients who have PDGFR α expressing tumors, since PDGFR α is a target of sorafenib and this is the most promising subgroup in preclinical models. A second interim analysis will be performed once enough patients with PDGFR α expressing tumors have been accrued, to determine if the drug combination is worth pursuing in this specific patient population.

2 OBJECTIVES

2.1 Primary Objective

2.1.1 Determine the efficacy of the combination of sorafenib, valproic acid, and sildenafil, in terms of 6-month PFS in high-grade glioma.

2.2 Secondary Objectives

2.2.1 Determine the efficacy of the combination of sorafenib, valproic acid, and sildenafil, in terms of 6-month PFS in high-grade glioma patients who are evaluable for response and who have tumors that express PDGFR α .

2.2.2 Evaluate the overall response rate, based on Response Assessment in Neuro-Oncology (RANO) criteria or Macdonald criteria, to the drug combination in patients

who are evaluable for response (those who express PDGFR α and those who do not).

- 2.2.3 Evaluate the overall response rate, based on RANO or Macdonald criteria, to the drug combination in PDGFR α expressing tumors in patients who are evaluable for response.
- 2.2.4 Determine the efficacy of the drug combination, in terms of 12-month survival and median overall survival in patients who are evaluable for response (those who express PDGFR α and those who do not).
- 2.2.5 Determine the efficacy of the drug combination, in terms of 12-month survival and median overall survival in high-grade glioma patients who are evaluable for response and who have tumors that express PDGFR α .
- 2.2.6 Evaluate the safety and toxicity of the drug combination.

■ [REDACTED]

■ [REDACTED]

3 STUDY DESIGN

3.1 General Description

The study is a single-center, open-label phase 2 study, with an early stopping rule in place for safety. The trial will include patients with recurrent or progressive high-grade glioma. The trial will be conducted in an adaptive design, with a Simon's mini-max 2-stage design (35) incorporating an interim analysis for efficacy. If efficacy endpoints are not reached, the trial focus will be narrowed to include only the subgroup of patients whose tumors express PDGFR α . The trial will continue with this cohort in a second Simon's mini-max 2-stage design, with an additional interim efficacy analysis of this subgroup.

3.2 Primary Endpoint

Proportion of patients evaluable for response, regardless of tumor PDGFR status, with 6-month PFS defined as the time from the first day a patient receives study treatment until time of progression per RANO or Macdonald criteria or death, whichever occurs first.

3.3 Secondary Endpoints

- 3.3.1 Proportion of patients evaluable for response, with tumors that express PDGFR α , with 6-month PFS defined as the time from the first day a patient receives study treatment until time of progression per RANO or Macdonald criteria or death, whichever occurs first.
- 3.3.2 Overall response rate (CR+PR), using RANO or Macdonald criteria, in patients evaluable for response regardless of tumor PDGFR status

- 3.3.3 Overall response rate (CR+PR), using RANO or Macdonald criteria, in patients who are evaluable for response and who have tumors that express PDGFR α .
- 3.3.4 Proportion of patients evaluable for response, regardless of tumor PDGFR status, who are alive at 12 months after the first day a patient receives study treatment. OS defined as the time from the first day a patient receives study treatment until death by any cause.
- 3.3.5 Proportion of patients evaluable for response with tumors that express PDGFR α who are alive at 12 months after the first day a patient receives study treatment. OS defined as the time from the first day a patient receives study treatment until death by any cause.
- 3.3.6 AEs using NCI Common Terminology Criteria for Adverse Events, Version 4.0 (CTCAE v4.0).

4 PATIENT SELECTION

4.1 Inclusion Criteria

A patient must meet all of the following inclusion criteria to be eligible to participate in the study:

- 4.1.1 Pathologically confirmed high-grade glioma (WHO grade 3 or 4), with documented CT or MRI progression or recurrence. Biopsy is also an acceptable method of confirming progression. If initial tumor was grade 2 glioma, histological confirmation of high-grade recurrence is required.
- After first interim analysis, if the study proceeds to enrollment of selected patients (only those who have PDGFR α -positive tumors), patients will be pre-registered for PDGFR α analysis and registered to the combination treatment schema only if PDGFR α -positive and all other enrollment criteria are met.
- 4.1.2 Measurable or evaluable disease by RANO (MRI) or Macdonald (CT) criteria (see Section [10.2](#)).
- 4.1.3 Fixed or decreasing dose of corticosteroids (or no corticosteroids) for at least 1 week prior to cycle 1 day 1.
- 4.1.4 Age \geq 18 years.
- 4.1.5 At least 12 weeks since the completion of radiation therapy to a total of \geq 50 Gy.

4.1.6 ECOG performance status of 0, 1, or 2 ([Appendix 1](#)).

4.1.7 Clinical laboratory parameters:

- WBC $\geq 3,000/\text{mm}^3$
- ANC $\geq 1,500/\text{mm}^3$
- Platelets $\geq 100,000/\text{mm}^3$
- Hgb ≥ 8.5 g/dL
- AST, ALT ≤ 3 x upper limit of normal (ULN) for the laboratory
- Total bilirubin ≤ 1.5 x ULN for the laboratory (total bilirubin criteria may be waived if a patient has documented Gilbert's disease)
- Creatinine clearance (CrCL) ≥ 30 mL/min as calculated by the standard Cockcroft-Gault equation ([Appendix 2](#))

4.1.8 Women of childbearing potential must have a negative serum pregnancy test performed within 7 days prior to the start of treatment.

4.1.9 Women of childbearing potential and men must agree to use a medically accepted form of birth control for the duration of study participation and for 2 months following completion of study treatment.

4.1.10 Ability to understand and the willingness to sign a written informed consent document.

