10 MEASUREMENT OF EFFECT

10.1 Definitions

Evaluable for toxicity. All patients will be evaluable for toxicity from the time of their first treatment with sorafenib and/or valproic acid and/or sildenafil.

Evaluable for qualifying toxicities for the safety lead-in. Only those patients who have completed the first cycle of therapy (or have experienced a qualifying toxicity prior to the end of the first cycle) will be evaluable for the safety lead-in. Qualifying toxicities will be defined in the first cycle only. Patients must have completed twice-daily sorafenib dosing for at least 21 out of the first 28 days to be considered to have had sufficient exposure to the regimen for qualifying toxicity evaluation. Patients who are not evaluable for the qualifying toxicity assessment for the safety lead-in will be replaced.

Evaluable for qualifying toxicities for the early stopping rule after the safety lead-in. Patients who have initiated the first cycle of therapy will be considered evaluable for the early stopping rule. Qualifying toxicities will be defined in the first cycle only. Patients who are not evaluable for the qualifying toxicity assessment for the early stopping rule will not be replaced unless they were included in the safety-lead in.

Evaluable for objective response. Patients who have been treated with the combination of twice-daily sorafenib and valproic acid for a minimum of 28 days, and have had their disease re-evaluated, will be considered evaluable for response. These patients will have their response classified according to the definitions stated below. Patients who do not complete study dosing for at least 28 days, or those who do not have their disease re-evaluated following initiation of the combination of sorafenib and valproic acid, will be replaced to ensure that a sufficient number of patients will be available for response evaluation.

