10.2.1 Neurologic Exam Status

Table 12. Neurologic Exam Status as Compared to Pre-Treatment Exam

Status	Criteria
Better	No new neurologic deficits. Must be on stable or decreasing dose of steroids, with stable to improved ECOG performance status
Worse	New neurologic deficits, declining ECOG performance status, or requiring increasing dose of steroids to remain stable

10.2.2 MRI Assessment: Based on Response Assessment in Neuro-Oncology working group (RANO) criteria [\(37\)](#).

Table 13. RANO Criteria

Response	Criteria
Complete Response	Requires all of the following: Complete disappearance of all enhancing measurable and non-measurable disease sustained for at least 4 weeks; no new lesions; stable or improved non-enhancing (T2/FLAIR) lesions; and with patient off corticosteroids or only on physiological replacement doses. Requires repeat MRI in 4 weeks for confirmation.
Partial Response	Requires all of the following: $\geq 50\%$ decrease, compared with baseline, in the sum of products of perpendicular diameters of all measurable enhancing lesions sustained for at least 4 weeks; no progression of non-measurable disease; no new lesions; stable or improved non-enhancing (T2/FLAIR) lesions on the same or lower dose of corticosteroids compared to baseline scan; and with patient on a dose corticosteroids not greater the dose at the time of baseline scan, and is stable or doing better clinically. Requires repeat MRI in 4 weeks for confirmation.
Stable Disease	Stable disease occurs if the patient does not qualify for complete response, partial response, or progression, and requires the following: Stable non-enhancing (T2/FLAIR) lesions on the same or lower dose of corticosteroids compared with baseline scan and clinically stable status. In the event that the corticosteroid dose was increased for new symptoms and signs without confirmation of disease progression on neuroimaging, and subsequent follow-up imaging shows that this increase in corticosteroids was required because of disease progression, the last scan considered to show stable disease will be the scan obtained when the corticosteroid dose was equivalent to the baseline dose.

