Progressive Disease	Progression is defined as any of the following: $\geq 25\%$ increase in the sum of the products of perpendicular diameters of enhancing lesions, on stable or increasing doses of steroids; a significant increase in non-enhancing (T2/FLAIR) on stable or increasing dose of steroids compared with baseline scan or best response after initiation of therapy; the appearance of new lesions; clear progression of non-measurable lesions; definite clinical deterioration not attributable to other causes apart from tumor or to decreases in corticosteroid dose.

10.2.3 Contrast-enhanced CT Assessment: Based on Macdonald Criteria (38).

Table 14. Macdonald Criteria

Response	Criteria
Complete Response	Requires all of the following: complete disappearance of all enhancing measurable and non-measurable disease sustained for at least 4 weeks; no new lesions; no corticosteroids; and stable or improved clinically.
Partial Response	Requires all of the following: $\geq 50\%$ decrease compared with baseline in the sum of products of perpendicular diameters of all measurable enhancing lesions sustained for at least 4 weeks; no new lesions; stable or reduced corticosteroid dose; and stable or improved clinically.
Stable Disease	Requires all of the following: does not qualify for complete response, partial response, or progression; and stable clinically.
Progression	Defined by any of the following: $\geq 25\%$ increase in sum of the products of perpendicular diameters of enhancing lesions; any new lesion; or clinical deterioration.

*Table from (37)

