10.3 Considerations for Patients with Multifocal Disease

For patients with multifocal disease, progressive disease is defined as $\geq 25\%$ increase in the sum of the products of perpendicular diameters of enhancing lesions compared with the smallest tumor measurements after the initiation of therapy. The appearance of a new lesion or unequivocal, progression of non-target lesions will also be considered progression.

Partial response is defined as a $\geq 50\%$ decrease, compared with baseline, in the sum of products of perpendicular diameters of all measurable enhancing lesions sustained for at least 4 weeks, with stable or decreasing corticosteroid dose and with stable neurologic exam.

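### Patients with only non-measurable disease count in the response-rate denominator but can respond only by complete response, which dilutes the CR+PR rate relative to patients with measurable disease

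*Combined protocol and SAP*

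**What the plan says.** Entry: criterion 4.1.2 requires "Measurable or evaluable disease by RANO (MRI) or Macdonald (CT) criteria". Measurable and evaluable are alternatives, so a measurable lesion is not needed. The criterion points to Section 10.2, which defines neither term.

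Denominator: Section 10.1 states that patients treated with sorafenib and valproic acid "for a minimum of 28 days, and have had their disease re-evaluated, will be considered evaluable for response". It sets no condition on measurability. Endpoint 3.3.2 is "Overall response rate (CR+PR), using RANO or Macdonald criteria, in patients evaluable for response regardless of tumor PDGFR status", and 3.3.3 is the same rate in patients with PDGFRα-expressing tumors.

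Numerator, PR: Table 13 (RANO) and Table 14 (Macdonald) both require at least a 50% decrease "in the sum of products of perpendicular diameters of all measurable enhancing lesions sustained for at least 4 weeks". Section 10.3, for multifocal disease, also takes the decrease over the sum "of all measurable enhancing lesions sustained for at least 4 weeks, with stable or decreasing corticosteroid dose".

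Numerator, CR: Table 13 requires "Complete disappearance of all enhancing measurable and non-measurable disease sustained for at least 4 weeks", and Table 14 has the same requirement. CR is thus open to a patient whose enhancing disease is all non-measurable.

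Coding and analysis: Section 13.7 codes stable disease as non-response and makes no exception for non-measurable disease. Section 13.5 plans estimates with 95% confidence intervals for the whole population and the PDGFRα-expressing cohort. No analysis is restricted to measurable disease.

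**The concern.** The denominator and the PR definition do not match. Suppose a patient has only non-measurable enhancing disease and the tumor shrinks markedly without disappearing. No PR definition in the protocol can be applied, so the best response is stable disease at most, coded as non-response. The reported rate then depends partly on how many such patients enrol, and not only on what the drugs do.

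Such patients are plausible under the entry criteria. Section 4.1.1 accepts biopsy as confirmation of progression, and Section 4.2.7 bars major surgery only in the 2 weeks before treatment, so a patient whose recurrence has been resected could enter.

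What is at stake is the interpretation of response. Section 1.8 plans to correlate PDGFRα expression with response, and says that later gene expression profiling, considered in the light of responses, may help to characterize a phase 3 population. In that correlation, a patient who could not be scored PR would look like a biological non-responder. The groups are small: at the 30–40% positivity in Section 13.2, 33 unselected patients include about 10 to 13 PDGFRα-positive patients (0.30 × 33 = 9.9; 0.40 × 33 = 13.2), where one patient is worth about 8 to 10 percentage points.

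**Working it through.** **The plan's own figures.** The documents give no expected response rate for this trial and no share of patients with non-measurable disease, so there is no response-rate figure to reproduce. The only design calculation is for 6-month PFS (Section 13.2: p0 = 0.20, p1 = 0.40, stop at 3 or fewer of 16, success at 11 or more of 33). An exact binomial calculation gives type I error 0.0475 and power 0.811, within the stated 5% and 80%. Nothing in it depends on PR.

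**Formula.** Let
- s = share of response-evaluable patients with only non-measurable disease (not in the documents; assumed),
- R = CR+PR rate in patients with measurable disease (assumed; for scale, Section 1.7 reports PR rates of 3–12% in earlier sorafenib studies),
- c = CR rate in patients with only non-measurable disease (not in the documents; assumed).

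Reported rate = (1 − s) × R + s × c.

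Absolute shortfall against R = s × (R − c).

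Relative shortfall = s × (1 − c/R), which is at most s and equals s only at c = 0.

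**Results at R = 12%.**

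| s | reported, c = 0 | shortfall (points) | reported, c = 2% | shortfall (points) |
|---|---|---|---|---|
| 10% | 10.8% | 1.2 | 11.0% | 1.0 |
| 20% | 9.6% | 2.4 | 10.0% | 2.0 |
| 30% | 8.4% | 3.6 | 9.0% | 3.0 |

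Worked line: s = 20%, c = 2% gives 0.80 × 12% + 0.20 × 2% = 9.6% + 0.4% = 10.0%. The relative shortfall is 2.0/12 = 16.7%, not 20%.

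**Results at R = 3%, c = 0.** For s = 10% to 30% the reported rate is 2.7% to 2.1%, a shortfall of 0.3 to 0.9 points.

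**Effect of restricting the denominator.** Take 4 responders in 33: 12.1%, exact 95% CI 3.4–28.2%. If 7 of the 33 had only non-measurable disease and none of those had a CR, the rate in measurable patients is 4/26 = 15.4%, CI 4.4–34.9%. The estimate rises by 3.3 points, and the interval widens from 24.8 to 30.5 points (30.5/24.8 = 1.23, so 23% wider).

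**Primary endpoint.** Progression does not need a measurable lesion: Table 13 includes "clear progression of non-measurable lesions", and Table 14 includes any new lesion and clinical deterioration. Six-month PFS can therefore be scored in these patients.

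**The case against.** The strongest case on the other side has four parts.

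- The share is unknown. Section 4.1.1 asks for progression or recurrence documented on imaging, with biopsy also acceptable, and nothing shows how many patients would lack a measurable lesion. This stands: s may be zero, and every value of s above is an assumption.
- The effect is small against the precision. With 33 patients one responder is worth 3.0 points, more than the shortfall at s = 10–20%. This stands for the whole cohort. It limits the size but does not repair the mismatch.
- No decision rests on it. Response rate has no null value, target or power, and both Simon designs and the move to PDGFRα-positive enrolment use 6-month PFS. This stands.
- The rate among all response-evaluable patients is exactly what the protocol defines, and it is low only against a different population. This stands too. It is a reason to keep that rate and add a second one, not to replace it.

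A reader might also infer that the result is biased against the 3–12% PR rates in Section 1.7. The documents do not support that: those rates are background, Section 13 plans no comparison with them, and the protocol does not say whether those studies required measurable disease.

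**Conclusion.** The mismatch is real and follows from the text: entry without a measurable lesion, a denominator that ignores measurability, and three PR definitions that all require it. The CR+PR rates in 3.3.2 and 3.3.3 are diluted, relative to patients with measurable disease, by s × (R − c). At R = 12% and s = 10–30% this is 1.0 to 3.6 points for c between 2% and 0; at R = 3% and c = 0 it is 0.3 to 0.9 points. These sizes rest on assumed s, R and c.

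Two stronger readings are tempting, and neither holds. One is that these patients can never count as responders; CR in both tables covers non-measurable enhancing disease. The other is that the reported rate is too low by their share. The share is only an upper bound on the relative shortfall, reached if none of them has a CR, and it is not an absolute shortfall: a 20% share at R = 12% costs at most 2.4 points, not 20.

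One matter stays open because evaluable disease is undefined. If it includes patients with only non-enhancing disease, there is no enhancing lesion to disappear, and the text does not settle how CR would be scored.

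The consequence is confined to a secondary, descriptive endpoint and the exploratory correlation in Section 1.8.

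**What to change.** - In 3.3.2, 3.3.3 and 13.5, prespecify the CR+PR rate with its 95% CI among response-evaluable patients with at least one measurable enhancing lesion at baseline. Report it alongside the all-evaluable rate as now defined.
- Use the measurable-disease set for the correlation of PDGFRα with response.
- Report best response separately for patients with only non-measurable disease, using the categories already in Tables 13 and 14, and give their number in each cohort.
- State in 4.1.2 or 10.2 what counts as measurable and as evaluable disease, including whether non-enhancing disease alone qualifies.
- Leave 6-month PFS, the sample size and the Simon rules as they are.

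The cost is wording and one extra row in the response tables. Baseline lesion measurements are already needed to apply the response criteria, so no new visits, scans or patients are required. The added rate has a wider interval because its denominator is smaller, as in the 4/33 against 4/26 example, which is a further reason to show both rates.

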4.2 Exclusion Criteria

A patient who meets any of the following exclusion criteria is ineligible to participate in the study:

4.2.1 Investigational agent within 4 weeks of first dose of study treatment.

4.2.2 Prior bevacizumab or tyrosine-kinase inhibitor.

4.2.3 History of allergic reactions or intolerance to any of the required agents on the study.

4.2.4 Any condition that would prohibit patient from initiating valproic acid. Current or prior valproic acid treatment is allowed (do not need to be \geq LLN for laboratory for enrollment). See Section [6.2.7](#) for details on valproic acid titration prior to initiation of study therapy.

4.2.5 Seizure disorder necessitating the use of EIAEDs. Efforts may be made by the treating physician to change the antiepileptic drug from another agent to valproic acid or non-EIAED prior to excluding the patient from study.

4.2.6 Contraindication to antiangiogenic agents, including:

- Bronchopulmonary hemorrhage/bleeding event \geq grade 2 (NCI Common Terminology Criteria for Adverse Events [CTCAE] version 4.0) within 4 weeks or less prior to first dose of study drug.
- Any other hemorrhage/bleeding event \geq grade 3 (CTCAE v4.0) within 4 weeks or less prior to first dose of study treatment.

- Radiological evidence of any intracranial hemorrhage within the 4 weeks or less prior to first dose of study treatment.
 - History of significant intratumoral, intracerebral, or subarachnoid hemorrhage.
 - Serious non-healing wound, ulcer, or bone fracture.
 - Documented bowel perforation within 6 months of the start of study treatment.
- 4.2.7 Major surgery within 2 weeks of the start of study treatment, or ongoing complications from surgeries performed previously.
- 4.2.8 Clinically significant cardiac disease, including major cardiac dysfunction, such as uncontrolled angina, clinical congestive heart failure with New York Heart Association (NYHA) class III or higher ([Appendix 3](#)), ventricular arrhythmias requiring anti-arrhythmic therapy, recent (within 6 months) myocardial infarction or unstable coronary artery disease.
- 4.2.9 Systolic blood pressure (BP) > 160 mm Hg or diastolic pressure > 100 mm Hg despite optimal medical management.
- 4.2.10 History of priapism.
- 4.2.11 Known history of retinitis pigmentosa.
- 4.2.12 Known mitochondrial disorder caused by mutations in mitochondrial DNA polymerase γ .
- 4.2.13 Arterial thromboembolic or embolic events such as myocardial infarction, cerebrovascular accident, including transient ischemic attacks within 6 months prior to first study treatment.
- 4.2.14 Serious uncontrolled infection > grade 2 (CTCAE v4.0).
- 4.2.15 Known HIV positivity.
- 4.2.16 Unable to swallow medication or suspected malabsorption.
- 4.2.17 Patients on chronic nitrate therapy or alpha-blockers.
- 4.2.18 Exclude persons who require ongoing administration of STRONG CYP3A4 inhibitors and/or STRONG CYP3A4 inducers and/or STRONG CYP2C9 inhibitors. Examples of clinical inhibitors and clinical inducers for P450-mediated metabolisms and classification of strong, moderate, and weak interactions are available through the FDA website, Table 3-2 and 3-3:
<http://www.fda.gov/Drugs/DevelopmentApprovalProcess/DevelopmentResources/DrugInteractionsLabeling/ucm093664.htm>
- 4.2.19 Women who are pregnant or nursing.
- 4.2.20 Persistent heart rate (HR) < 50 or > 120 beats per minute (bpm).
- 4.2.21 QTc > 480 ms (grade 2 or greater) on screening ECG*.

* If baseline QTc on screening ECG meets exclusion criteria on screening assessment:

- Check potassium and magnesium levels
- Correct any identified hypokalemia and/or hypomagnesemia and repeat ECG to confirm exclusion of patient due to QTc
- For patients with a HR 60-100 bpm, no manual read of QT is required.
- For patients with baseline HR < 60 or > 100 bpm, manual read of QT by cardiologist is required using Fridericia correction.

4.2.22 Other condition(s) that in the opinion of the investigator might compromise the objectives of the study.

